### **neurostatus forum**

Forum for a standardised, quantified neurological examination and assessment of Kurtzke's Functional Systems and Expanded Disability Status Scale in Multiple Sclerosis

[www.neurostatus.net](http://www.neurostatus.net)

## APPENDIX H. INSTRUCTIONS FOR THE TIMED 25-FOOT WALK

### Description

The Timed 25-Foot Walk is a quantitative measure of lower extremity function. The patient is directed to 1 end of a clearly marked 25-Foot course and is instructed to walk 25 feet as quickly as possible, but safely. The task is immediately administered again by having the patient walk back the same distance. Patients may use assistive devices when doing this task.

### Materials Needed

Stopwatch, clipboard, Timed 25-Foot Walk Record Form, marked 25-Foot distance in an unobstructed hallway, assistive device (if needed)

### Time Limit Per Trial

3 minutes (180 seconds) per trial.

### Discontinue Rules

If the patient cannot complete Trial 2 of the Timed Walk after a 5-minute rest period.

If the patient cannot complete a trial in 3 minutes.

### Administration

#### Trial 1

Make sure that the stopwatch is set to 0:00. For the Timed 25-Foot Walk, the patient should be directed to 1 end of a clearly marked 25-Foot course (clearly defined on the floor or on the wall) and instructed to stand just behind the starting line. Point out where the 25-Foot course ends, then instruct the patient as follows: *"I'd like you to walk 25 feet as quickly as possible, but safely. Do not slow down until after you've passed the finish line. Ready? Go."*

Begin timing when the lead foot is lifted and crosses the starting line. The examiner should walk along with the patient as s/he completes the task. Stop timing when the lead foot crosses the finish line. The examiner should then record the patient's walk time to within 0.1 second, rounding as needed. Round up to the next tenth if hundredth's place is > (greater than or equal to) .05, round down if hundredth's place is <.05 (eg, 32.45" would round to 32.5" but 32.44" would round to 32.4"). Once the time is recorded, be sure to reset the stopwatch.

#### Trial 2

After completing the first timed walk, position the patient just behind the line where s/he is not standing, repeat the same instructions, and have the patient complete the walk again.

### Assistive Devices

The goal is to have the patient use the same assistive device at each study visit. The Treating Neurologist will select an assistive device at the beginning of the study for each patient that needs 1, keeping in mind that the patient may deteriorate modestly during the trial.

In general, patients should use their customary assistive device(s), NOT the least assistance possible to complete the test. For patients with significant gait impairment, the Treating Neurologist should have the patient use a rolling walker even if this is not the patient's customary

device. In general, non-wheeled walkers should not be used. If a patient does use an assistive device, this should be noted on the Record Form.

### **Completing the Record Form**

Record any circumstances that you believe may have affected the patient's performance. These are factors that may have affected the trial but were not severe enough to necessitate repetition of the trial. Examples include, but are not limited to, the following:

- The patient had a cold or reports not feeling well.
- The patient tripped but did not fall.

If a situation arises that necessitates the repetition of a trial, indicate the reason a trial had to be repeated on the Record Form. Examples of reasons to repeat a trial include, but are not limited to, the following:

- The patient fell during the walk.
- Examiner forgot to start or stop stopwatch.
- Examiner forgot to reset stopwatch in between trials.
- The patient stopped to talk to someone while walking, or another person/thing somehow interfered with walk.

Record only the times for the 2 **successfully completed** trials of the Timed 25-Foot Walk. If the patient could not complete 1 or both of the trials of the Timed 25-Foot Walk, record this in the appropriate section of the Record Form. For example, if the patient's disease has progressed and/or physical limitations prohibit him or her from completing the trial, you should indicate "Unable to complete trial due to physical limitations" and record any specifics that you can observe (ie, patient in a wheelchair now and unable to walk, etc.). If the patient did not complete a trial for any other reason, specify this as well (eg, patient fell and was too fatigued to complete another trial, patient refused to complete trial).

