5.5. Handling Withdrawals and Missing Data

If a patient performs an early termination (ET) visit, then this ET visit will be considered as next scheduled visit for the summaries and analyses of the following items: MRI data (following week 36 only), T25FW, 9HPT, EDSS, SDMT, CVLT (following week 24 only), BVMT (following week 24 only), LCVA and MSWS-12. Listings will present early termination visit records as they appear in the data.

The total EDSS score is composed of eight functional system scores (FSS). If any of the FSS are missing at a particular time point, the total EDSS score will also be considered missing at that time point.

Missing dates will be imputed as follows for data related to PPMS history (see Section 6.3):

1. In cases where only day is missing/unknown, then the 1st of the month will be imputed.
2. In cases where both day and month are missing/unknown, then the 1st of January will be imputed.
3. In cases where the whole date is missing, the date will be considered as missing.
4. In listings, dates will appear as they are in the data (i.e., missing/unknown values as “UNK”).

The MSWS-12 score will be calculated as the sum of the 12 items of the questionnaire. In case there are one or two items missing, the mean of the non-missing items per patient will be imputed. In a case with more than 3 items missing, the total score will be considered missing as well. Listings will present the item data as appears in the data.

Following CDP related endpoints definition (see Section 7.4.1), a CDP cannot be confirmed during a protocol defined relapse, whereas relapse occurrence is identified by relapse onset and approximate stabilization date. If a relapse onset is partial then assessment date of the relapse will be used instead. If a relapse stabilization date is partial, then the last day of the relevant month will be used in that date. Similar imputation of relapse onset and stabilization dates will be done for definition of protocol defined relapses (see Section 7.5.18) if needed. Listings will present relapse related information as appears in the data.

For all other variables, only the observed data from the patients up to study completion or study withdrawal will be used in the statistical analyses, i.e., there is no plan to impute missing data for other variables.

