7.4.2. Time to CDP event as measured by EDSS or T25FW

Time to CDP as measured by EDSS or T25FW will be defined by reaching at least 1 of the following 2 types of event for each individual:

- An increase from baseline in EDSS score (≥ 1 point from baseline EDSS, if EDSS at entry is ≤ 5.0 or increase of ≥ 0.5 point, if EDSS at entry is ≥ 5.5), confirmed after at least 12 weeks, **or**
- An increase of at least 20% from baseline in the T25FW test, confirmed after at least 12 weeks

Progression cannot be confirmed during a protocol defined relapse. A similar algorithm to that described for CDP as measured by EDSS will be used for definition and censoring rules of this variable (see Section 7.4.1).

T25FW will be calculated as a mean time of two T25FW trials at each visit. In cases when a patient could not complete a T25FW trial due to the physical limitations a value of 180 seconds will be assigned for that trial (this is the maximal possible value for the T25FW test).

Time to CDP as measured by EDSS or T25FW, confirmed after at least 12 weeks will be analyzed using the ITT population and will include data from all the study assessments done up to seven days after the date of last dose of the study drug (all the following assessments will be excluded from this analysis). This analysis will be performed using baseline adjusted Cox's proportional hazards regression model (SAS® PROC PHREG) in which 1 contrast for comparing laquinimod 0.6 mg to placebo will be constructed. In addition to treatment group, categorical EDSS at baseline (≤ 4.5 or > 4.5), age at baseline, T25FW at baseline, natural logarithm of T2 lesion volume at baseline, and CGR will be used as covariates. The SAS code for this analysis is as follows:

```

PROC PHREG;
  CLASS ARM EDSSBASE CGR;
  MODEL TIME_TO_PROGRESSION*CENSOR(1,2,3)=ARM EDSSBASE T25BASE AGE LT2BASE CGR /
COVB RL;
  CONTRAST 'Laq 0.6 to Plb' ARM 1 / ESTIMATE=EXP;
  WHERE ARM in ('Laquinimod 0.6 mg', 'Placebo'); RUN;

```

In case the above model will not converge due to CGR variable, then CGR will be removed from the model.

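### A timed walk lost to a fall and fatigue is recorded outside the class that SAP 7.4.2 scores as 180 seconds, and the SAP does not say how such a trial or its visit is scored

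*Protocol*

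**What the plan says.** **Recording (protocol Appendix H).** The rater records times for completed trials only. A trial is marked as not completed for physical limitations when disease progression or "physical limitations prohibit him or her from completing the trial". Other causes form a separate class: "did not complete a trial for any other reason, specify this as well (eg, patient fell and was too fatigued to complete another trial". Refusal is the other example given there. A fall alone does not end the test, because "The patient fell during the walk" is a listed reason to repeat a trial. The Discontinue Rules foresee the later failure ("If the patient cannot complete Trial 2 of the Timed Walk after a 5-minute rest period") but attach no score to it. The time limit is "3 minutes (180 seconds) per trial".

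**Scoring (SAP 7.4.2).** The visit score is the mean of the two trials. "In cases when a patient could not complete a T25FW trial due to the physical limitations a value of 180 seconds will be assigned", described as the largest value the test can take. No other reason for non-completion is given a value.

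**Missing data (SAP 5.5).** After the listed special cases, none of which covers a missing T25FW trial: "For all other variables, only the observed data from the patients up to study completion or study withdrawal will be used in the statistical analyses". Protocol 9.4 says the same in general terms.

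**Half-complete visits.** SAP 7.5.1 and 7.5.2 say that a missing CVLT-II or BVMT-R trial makes the whole score missing. There is no such sentence for T25FW.

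**The concern.** Eligible patients have an EDSS of 3 to 6.5 and a pyramidal score of at least 2 or gait impairment from the legs. When such a patient falls and is then too tired to walk 25 feet again, that is a loss of the function the test measures. The plan has a value for a failed walk, but the recording instruction puts this case with refusals, where the value does not reach it. The missingness is informative, and the error runs one way: worsening is understated.

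The analyses exposed are secondary endpoint 2 (progression by EDSS or T25FW), secondary endpoint 3 (change in T25FW to week 48), the four-event progression endpoint (SAP 7.5.3), progression by T25FW alone (SAP 7.5.20), and the by-gender repeats of the two secondary endpoints.

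**Working it through.** **The plan's own figure.** Appendix H allows 3 minutes per trial: 3 × 60 = 180 s. This agrees with SAP 7.4.2.

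**One failed trial followed through the rules.** The documents give no walk times, so these are assumed: baseline 10 s, trial 1 = 11 s, a fall in trial 2, and the patient too fatigued to repeat. The 20% threshold is 1.2 × 10 = 12 s.

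| Reading | Visit score | At least 12 s? |
|---|---|---|
| Failed trial takes 180 s | (11 + 180)/2 = 95.5 s | yes |
| As written, completed trial used alone | 11 s (+10%) | no |
| As written, visit missing | none | not assessable |

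If both trials are lost this way, the visit is 180 s under the failure rule and missing as written.

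**Does the example depend on the walk time?** With trial 1 equal to baseline *b*, one trial at 180 s gives (*b* + 180)/2. This is at least 1.2*b* whenever *b* ≤ 180/1.4 = 128.6 s. At *b* = 5 s the mean is 92.5 s (+1750%); at *b* = 120 s it is 150 s (+25%). For almost any baseline, then, the choice of reading decides the 20% call at that visit when the completed walk is itself below threshold.

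**Effect on confirmed progression (algorithm in SAP 7.4.1, carried over to T25FW).**
- Condition 3 binds only visits at which the test was evaluated between onset *t* and *s* = *t* + 12 weeks. A missing visit there blocks nothing.
- Condition 4 accepts any non-relapse visit at or after *s*. A missing confirming visit passes confirmation to a later one, with the event still dated at *t*.
- A missing visit does harm when it would have been the onset, which is then dated later, or when no later visit exists, in which case the patient is censored at *t*.
- A low single-trial score can hide an onset. It breaks condition 3 if it falls before *s*, and fails to confirm at that visit if it falls at or after *s*.

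**Frequency.** None is given. With the SAP's 140 patients per arm, assumed rates of 0.5%, 1%, 2% and 5% of patients at one visit give 140 × rate = 0.7, 1.4, 2.8 and 7 patients per arm.

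**Illustration of size.** All values are assumed: 126 per arm, a 0.25 SD shift, a Wilcoxon test at one time point, 6,000 runs. Walking failures take the worst rank, except for a misfiled share, which is dropped.

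| Failures, drug / placebo | Share misfiled | Power, all at worst rank | Power, misfiled share dropped |
|---|---|---|---|
| 1% / 3% | 25% | 0.556 | 0.534 |
| 1% / 5% | 25% | 0.657 | 0.612 |
| 2% / 6% | 25% | 0.648 | 0.610 |
| 1% / 3% | 10% | 0.582 | 0.571 |
| 1% / 5% | 10% | 0.662 | 0.646 |
| 2% / 6% | 10% | 0.650 | 0.635 |
| 3% / 3% | 25% | 0.439 | 0.447 |

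The loss is about 2 to 5 points with a quarter misfiled and 1 to 2 points with a tenth. With equal failure rates there is no loss.

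**The case against.** SAP 7.4.2 does not cite the record form, and its wording could be read to cover a patient physically too fatigued to walk. The form itself is not in the documents; the two classes come from Appendix H's instructions and examples. That stands as far as it goes. But the SAP uses the form's own term for the first class, and Appendix H puts fall-and-fatigue outside it. Two defensible readings are a reason to settle the rule before unblinding.

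The case is also narrow. A fall normally leads to a repeat, a 5-minute rest is foreseen, and failures recorded as physical limitations already take 180 s. The primary endpoint is untouched, and endpoints 2 and 3 are tested only after PBVC and EDSS progression succeed, in a Phase 2 proof-of-concept trial. All of this stands and limits the weight of the point.

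Three stronger readings are tempting but unsupported:
- **That these walks, or the patients, drop out of the endpoints.** If the other trial was completed, the visit may keep a score. Other visits stay in the repeated-measures model, and EDSS still counts in the composite.
- **That a missing value blocks confirmation.** Conditions 3 and 4 do not work that way, as shown in the working.
- **That power falls substantially.** This requires dropping every walking failure, although those due to physical limitations are already scored, and an assumed excess of failures on placebo. The documents supply no rate for either.

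**Conclusion.** The gap is real on the text. Read with Appendix H, a trial lost because the patient was too fatigued to walk again after a fall receives no value, and the SAP leaves open whether the visit is the single completed walk or missing. Either outcome can understate worsening in the T25FW endpoints. At the affected visit the choice can reverse the 20% call.

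Across the trial the effect is probably small, and its size cannot be computed from the documents. It rests on how often such walks occur, how raters file them, and whether they differ between arms. The case for the change is correct and prespecified measurement, with no promise of added power.

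**What to change.** Leave Appendix H as it is: changing the rater categories late in the trial would make recorded reasons inconsistent across visits. Before unblinding, add to SAP 7.4.2, and apply to 7.4.3, 7.5.3 and 7.5.20:

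1. A trial takes 180 s when the recorded reason, classified at the blinded data review, shows that the patient was physically unable to complete it. This includes being too fatigued to repeat after a fall.
2. Refusal, examiner error and purely accidental interruption leave the trial missing. A fall alone does not earn 180 s.
3. State how a visit with one completed and one missing trial is scored.

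Sections 7.5.3 and 7.5.20 point to 7.4.3 for the T25FW definition, but the scoring rule stands in 7.4.2. Correct the reference at the same time.

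The cost is a few sentences and a small addition to the blinded data review meeting that SAP 4.5 and 5.4 already plan; Appendix H already asks for the reason to be specified. The downside is that an occasional fall unrelated to MS will be scored as a failure. Ranking and the 20% threshold limit the influence of the extreme value.

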## APPENDIX I. INSTRUCTIONS FOR THE 9-HOLE PEG TEST

### Description

The 9-HPT is a quantitative measure of upper extremity (arm and hand) function. The 9-HPT is the second component of the MSFC to be administered. Both the dominant and non-dominant hands are tested twice (two consecutive trials of the dominant hand, followed immediately by two consecutive trials of the non-dominant hand). It is important that the 9-HPT is administered on a solid table (not a rolling hospital bedside table) and that the 9-HPT apparatus be anchored.

### Materials Needed

9-HPT Apparatus, Anchor, stopwatch, clipboard, 9-HPT Record Form

### Time Limit per Trial

5 minutes (300 seconds) per trial

### Discontinue Rules

1. If the subject cannot complete one trial of the 9-HPT in 5 minutes.
4. If the subject cannot complete a trial with his or her dominant hand within 5 minutes, move on to the trials with the non-dominant hand.
5. If the subject cannot complete a trial with his or her non-dominant hand, end the test.

### Administration

#### Dominant Hand Trial 1

Make sure that the stopwatch is set to "0:00." Introduce this section by saying, "*Now, we're going to be measuring your arm and hand function.*" If this is the first visit, determine the dominant hand, ask, "*Are you right or left-handed?*" If the subject is not sure, then the dominant hand is determined by asking the subject which hand he/she did or does write with. Make a note of the dominant hand for subsequent instructions. Place the 9-HPT apparatus on the table, directly in front of the subject. Arrange the apparatus so that the side with the pegs is in front of the hand being tested and the side with the empty pegboard is in front of the hand not being tested. Secure with anchor.

Read the following instructions to the subject: "*On this test, I want you to pick up the pegs one at a time, using one hand only, and put them into the holes as quickly as you can in any order until all the holes are filled. Then, without pausing, remove the pegs one at a time and return them to the container as quickly as you can. We'll have you do this two (2) times with each hand. We'll start with your [DOMINANT] hand. You can hold the pegboard steady with your [NON-DOMINANT] hand. If a peg falls onto the table, please retrieve it and continue with the task. If a peg falls on the floor, keep working on the task and I will retrieve it for you. See how fast you can put all of the pegs in and take them out again. Are you ready? Begin.*"

Start timing as soon as the subject touches the first peg, and stop timing when the last peg hits the container. If a peg drops on the floor, the examiner may retrieve it and put it back in the peg box. However, if a peg drops onto the table, allow the subject to retrieve it.

Record the subject's time under "Dominant hand Trial 1." If the subject stops after having put all the pegs into the holes, prompt the subject to remove them as well by saying, *"And now remove them all."* If the subject begins to remove more than one peg at a time, correct him/her by saying, *"Pick up one peg at a time."*

### **Dominant Hand Trial 2**

After the first trial with the dominant hand, say, *"Good. Now, I'd like you to do the same thing again, once again using your [DOMINANT] hand. See how fast you can put all of the pegs in and take them out again. Ready? Begin."* Again, start timing as soon as the subject touches the first peg, and stop timing when the last peg hits the container. Record the subject's time under "Dominant hand Trial 2."

### **Non-Dominant Hand Trials 1 and 2**

After the second trial with the dominant hand, rotate the apparatus 180 degrees such that the side with the pegs is now in front of the non-dominant hand and the empty pegboard is in front of the dominant hand. Then say, *"OK. Now, I'd like you to switch and use your [NON-DOMINANT] hand. This time, you can use your [DOMINANT] hand to stabilize the pegboard. Ready? Begin."* Administer, time and record the two non-dominant hand trials following the procedures described above for dominant hand trials.

### **Completing the Record Form**

Record any circumstances that you believe may have affected the subject's performance. These are factors that may have affected the trial but were not severe enough to necessitate repetition of the trial. Examples include, but are not limited to, the following:

- The subject dropped a peg.
- The subject has a cold.
- The subject forgot eyeglasses and had difficulty seeing pegs.
- The subject talked during the task.
- The subject knocked entire apparatus on the floor.

If a trial is repeated, indicate this and specify the reason it had to be repeated. Examples of reasons to repeat a trial include the following:

The subject knocked entire apparatus on the floor.

- The examiner forgot to start or stop stopwatch.
- The examiner forgot to reset the stopwatch in between trials.

Record only the times for the two **successfully completed trials** for each hand on the 9-HPT. If the subject could not complete one or both of the trials for either hand of the 9-HPT, record this in the appropriate section of the Record Form. If the subject's disease has progressed and/or physical limitations prohibit him or her from completing the trial, the examiner should mark, "Unable to complete trial due to physical limitations." and then record any specifics that can be observed (eg, subject unable to use right hand, subject could not complete within time limit, etc.). If the subject did not complete a trial for any other reason, describe the specific circumstances (eg, subject refused).

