7.5.2. Change from baseline to week 48 in the BVMT-R score

BVMT-R scores will be calculated as a sum of total correct responses from three BVMT-R trials for each patient. If one of the three BVMT-R trials is missing, then the BVMT-R score will be considered missing as well.

Change from baseline in the BVMT-R score at week 48 will be analyzed by applying the same methodology used to analyze the change from baseline to week 48 in the CVLT-II score (see Section 7.5.1). Baseline CVLT-II score covariate will be replaced by BVMT-R at baseline. In addition, the BVMT-R scores and changes from baseline to each visit will be summarized using descriptive statistics.

When the study is completed, actual values of BVMT-R and changes from baseline to each visit will be summarized using descriptive statistics to include both part A and part B. Also, the changes from baseline to each visit will be analyzed using similar statistical methodology as presented in this section for changes from baseline to week 48 in BVMT-R test.

7.5.3. Time to CDP as measured by at least 1 of 4 types of events

Time to CDP as measured by at least 1 of 4 types of events for each individual will be defined if one of the below conditions holds (progression cannot be confirmed during a protocol defined relapse):

- An increase from baseline in EDSS score (≥ 1 point from baseline EDSS if EDSS at entry is ≤ 5.0 , or increase of ≥ 0.5 point if EDSS at entry is ≥ 5.5), confirmed after at least 12 weeks **or**
- An increase of at least 20% from baseline in T25FW test (see Section 7.4.3 for definition), confirmed after at least 12 weeks **or**
- An increase of at least 30% from baseline in the 9HPT test, confirmed after at least 12 weeks **or**
- A decrease of at least 20% from baseline in the SDMT score, confirmed after at least 12 weeks

9HPT will be calculated as a mean time of two 9HPT trials for both dominant and non-dominant hands (4 trials overall) at each visit. In cases when a patient could not complete a 9HPT trial due to the physical limitations a value of 300 seconds will be assigned for that trial (this is the maximal possible value for the 9HPT).

Similar algorithm to that described for CDP as measured by EDSS confirmed after at least 12 weeks will be used for definition and censoring rules of this variable (see Section 7.4.1).

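### Appendix I lists knocking the 9HPT apparatus to the floor both among events that need no repeat and among reasons to repeat, so a rater may either keep or replace the same spoiled time

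*Protocol*

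**What the plan says.** Protocol 6.4.4 sends the 9HPT rater to Appendix I for full instructions and says the rater need not be a physician or nurse. The last subsection of that appendix, Completing the Record Form, has two lists of examples.

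- The first is introduced with "These are factors that may have affected the trial but were not severe enough to necessitate repetition of the trial". Its last item is "The subject knocked entire apparatus on the floor".
- The second is introduced with "If a trial is repeated, indicate this and specify the reason it had to be repeated", followed by "Examples of reasons to repeat a trial include the following". Its first item is the same sentence.

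The text after the lists says "Record only the times for the two successfully completed trials for each hand on the 9-HPT". It does not say whether a trial finished after the apparatus has been picked up is a successful one.

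On the analysis side, SAP 7.5.3 states "9HPT will be calculated as a mean time of two 9HPT trials for both dominant and non-dominant hands (4 trials overall) at each visit". Its only special rule for a 9HPT trial assigns 300 seconds when physical limitations prevent completion. SAP 5.5 (missing data) adds nothing for a spoiled trial.

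**The concern.** Both lists are in the current protocol text, and they classify one event in opposite ways. A rater who keeps the time and a rater who repeats the trial can each point to Appendix I. Under Protocol 3.3.2 the rater does not see earlier 9HPT forms, so cannot match how a previous visit was handled.

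The score is used in three places, all exploratory:

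- the 30% worsening component of the four-event CDP (SAP 7.5.3);
- the baseline 9HPT covariate in that Cox model;
- the change in 9HPT to week 48 (SAP 7.5.14).

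The visit that matters most is baseline. A kept spoiled time there raises the reference against which every later 9HPT visit of that patient is judged, and can hide real worsening.

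**Working it through.** **1. Does anything else in the plan settle which list governs?**

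- The administration text of Appendix I deals with dropped pegs, not with the whole apparatus.
- The restriction to successfully completed trials is undefined for this event. A patient may still finish within the 5-minute limit once the apparatus is back on the table.
- The parallel timed-walk form in Appendix H draws a clear line. "The patient tripped but did not fall" is among the circumstances that need no repeat, and a fall during the walk is among the reasons to repeat. Those two lists share no item, which suggests that the 9HPT overlap is an editing error rather than intended discretion.

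The overlap is unresolved.

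**2. Effect of one kept spoiled trial on the visit score.** The plan gives no figure to reproduce here. The inputs are the four-trial mean and the +30% threshold, both from SAP 7.5.3. The multiple r, spoiled time over usual time, is an assumption. Let the usual time be T for all four trials:

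mean = (3T + rT)/4 = T × [1 + (r − 1)/4], so the score rises by (r − 1)/4.

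If the spoiled trial is at baseline, the later mean must reach 1.3 × T × [1 + (r − 1)/4]. The true worsening needed is therefore 1.3 × [1 + (r − 1)/4] − 1.

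| Assumed r | Rise in visit mean | True worsening needed if at baseline |
|---|---|---|
| 1.5 | 0.5/4 = 12.5% | 1.3 × 1.125 − 1 = 46.25% |
| 2 | 1/4 = 25% | 1.3 × 1.25 − 1 = 62.5% |
| 2.2 | 1.2/4 = 30% | 1.3 × 1.30 − 1 = 69% |
| 3 | 2/4 = 50% | 1.3 × 1.50 − 1 = 95% |

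**3. When does one spoiled follow-up trial reach the threshold?** Setting (r − 1)/4 = 0.30 gives r = 2.2. For assumed usual times of 20, 25, 30 and 40 s, that is a spoiled time of 44, 55, 66 and 88 s, all well under the 300 s limit.

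**4. Unequal hands.** With assumed times of 25 s (dominant) and 30 s (non-dominant), the four trials sum to 110 s. At r = 2.2 the rise is 1.2 × 25/110 = 27.3% if the spoiled trial is on the dominant hand and 1.2 × 30/110 = 32.7% if on the other. The equal-time figures are a fair guide.

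**5. Does reaching +30% at one follow-up visit make an event?** No. SAP 7.5.3 requires confirmation after at least 12 weeks. The algorithm it borrows from SAP 7.4.1 also requires any evaluation in between to meet the threshold.

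**The case against.** The strongest reply is that both lists sit under instructions for filling in a form. They give examples of what to write down, not commands to keep or repeat, and could be read as leaving the judgement of severity to a trained rater. The rule on successfully completed trials would also catch many spoiled times before they reach the database. Neither argument removes the problem. The same sentence stands in both lists with no severity qualifier, and the term that might act as a filter is not defined.

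Other parts of the reply do stand and set the size of the point:

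- A reader might infer that raters did in fact handle the event differently. The documents permit that; they do not show it.
- A reader might infer that a spoiled follow-up trial produces a false progression event. The confirmation rule prevents one such trial from doing so alone.
- The week-48 change in 9HPT is analysed on ranks with a Hodges-Lehmann estimate (SAP 7.5.14, using the method of 7.4.3), so the influence of one extreme time is bounded.
- A spoiled baseline affects one of four CDP components. EDSS, T25FW and SDMT can still register progression.
- Raters are blinded, so inconsistent handling should add noise rather than favour an arm.
- Appendix I requires "that the 9-HPT apparatus be anchored", so the event should be uncommon.

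**Conclusion.** The instruction contradicts itself and nothing in either document resolves it, so a rater may keep or replace the same spoiled 9HPT time. The practical effect is small. The main harm is a kept spoiled trial at baseline: over an assumed r of 1.5 to 3, the true worsening needed to register +30% rises to between about 46% and 95% for that patient. These figures rest on otherwise equal trial times and on assumed multiples; the documents give no 9HPT times and no frequency for the event.

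The reach is limited to the exploratory 9HPT change and the 9HPT component of the exploratory four-event CDP. The primary endpoint and the four secondary endpoints do not use the 9HPT. The documents do not support reading this as a source of false progression events from single visits, or of bias between arms. It is a minor point that is worth correcting because the correction is so cheap.

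**What to change.** Delete the item from the first list in Appendix I, so that the trial is repeated and only the repeat is recorded. This matches the timed-walk form, which repeats after a fall. Tell the raters.

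For trials already recorded with this event noted and no repeat, agree a rule at the data review that the SAP already schedules before unblinding (SAP 4.5 and 5.4). One option is to use the other trial of the same hand as that hand's value and then average the two hands, which keeps the equal weighting of hands in SAP 7.5.3. Simply averaging the three remaining trials would not. With assumed times of 25 s and 30 s, dropping one non-dominant trial gives (25 + 25 + 30)/3 = 26.7 s, whereas the same-hand rule gives (25 + 30)/2 = 27.5 s, the value with no spoiled trial.

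The cost is one deleted line, a rater notice, and a small check of comments already collected.
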